5.2.4 Pregnancy Test

Women of child-bearing potential (women who are not surgically sterile or postmenopausal (defined as amenorrhea for >12 months) must perform a pregnancy test (validated over-the-counter test) at Visit 1, before taking study required radiographs or CBCT scans to confirm that they are not pregnant. The test result must be documented in the source data. A woman who is pregnant or planning to become pregnant at any point during the study duration cannot be enrolled in this study and will be considered a screening failure.

If a woman becomes pregnant during the study, a protocol deviation form should be completed. The woman should be followed for the duration of the pregnancy, without the study required projected radiographs or CBCT until term, and the outcome of the pregnancy should be documented.

5.2.5 Full Mouth CBCT or Panoramic Radiograph + Local CBCT

A panoramic radiograph or full mouth CBCT scan must be available during screening to assess the complete dentition and for use in surgical planning. The screening panoramic radiograph or full mouth CBCT scan can be taken during the screening visit or be available from a previous date within 6 months of the implant surgery. If a panoramic radiograph is used for screening, then a localized CBCT scan is also required as a baseline.

5.2.6 Fabrication of Radiographic Media Holder

A radiographic media holder used to capture periapical (PA) radiographs throughout the study will be fabricated at screening. The device will be fabricated according to the instructions provided by Larheim and Eggen.³

5.3 Surgical Procedure (Visit 3)

This visit should be completed within 45 days of screening. In particular, the subject will have the following procedures and/or evaluations performed and documented at this visit:

- Dental and medical history
- Concomitant medication
- Adverse event check
- Oral hygiene
- Informed consent
- Tooth extraction
- Enrollment Inclusion/Exclusion criteria
- TN-SM device and implant placement
- Implant stability by clockwise torque with maximum at 20 Ncm to confirm stabilization
- Standardized periapical radiographs
- Intra-oral photographs

5.3.1 Tooth Extraction

Each potential subject will have the candidate site tooth extracted using standard procedures in an outpatient environment under local anesthesia. Curettage of the extraction socket will be performed to remove soft tissue remnants, including the periodontal ligament, granulation tissue, etc. Intraoral photographs will be captured. Subjects will pre-rinse with chlorhexidine mouthwash 0.12% for 30 seconds immediately prior to the surgery.

5.3.2 Extraction Site Enrollment Inclusion Criteria

- Approximately 2mm of apical bone is available for positive seating of the implant;
- Placement of the selected implant leaves an HDD greater than 2mm in at least two directions, (i.e., mesially, distally, buccally, or lingually) between the implant surface and the most coronal aspect of the osteotomy. (For the purpose of clarity, HDD is measured from the outer surface

of the implant to the inner aspect at the crest of the socket walls.)

5.3.3 Extraction Site Enrollment Exclusion Criteria

- Any implant site where there is a dehiscence or fenestration of buccal or lingual plates of bone greater than 5mm in any direction;
- Any implant site in which placement of the selected implant leaves an HDD greater than 5mm in any direction between the implant surface and the most coronal aspect of the osteotomy;
- Any site which provides primary implant stability after seating, as demonstrated by insertion torque of greater than or equal to 15 Ncm;
- Any site into which the implant is not or cannot be placed during the same visit as the extraction.

5.3.4 Surgery – TN-SM Device and Implant Placement

Each study subject will receive the TN-SM device to stabilize an implant in an outpatient environment. The procedure will be performed under local anesthesia following standard surgical and sterile techniques. After initial evaluation, surgical guides may be prepared in accordance with the surgeon's preference and standard practices. All implants will be placed in accordance with the IFU of the respective implant manufacturer, with possible departure related to the placement of the TN-SM. Prophylactic antibiotic treatment will be given according to the investigator's standard practice and shall be recorded. All prophylactic antibiotics and anesthesia given must be recorded on the Concomitant Medication Form. Prior to surgery, subjects should have teeth cleaned, if required, as per standard of care at the practice. Guided Bone/Tissue Regeneration (GBR/GTR) procedures will not be employed in this study as bone volume insufficiency and a large dehiscence are among Site Enrollment Exclusion Criteria.

The following is a detailed list of the procedures and measurements to be performed during the implant placement surgery visit:

- Following tooth extraction curette the socket;
- Prepare the implant bed according to the standard drilling sequence recommended by the implant manufacturer;
- Place the implant into the site according to standard procedures and apply the Extraction Site Enrollment Criteria to qualify the site.
- Assuming the implant has insufficient insertion torque, remove the implant. Prepare and apply the TN-SM device to the site according to the IFU Document 50001-00 (Appendix 1). Re-insert the implant to its preplanned seating position into apical bone. Consistent with the IFU,

additional TN-SM may be applied, if necessary, to fill any residual space between the implant surface and surrounding bone, up to the height of crestal bone. Care must be taken to ensure proper final position of the implant by use of standard measures that may include manual control or use of a prefabricated surgical guide.

- After the TN-SM device cures around the implant for 15 minutes, implant stabilization will be tested by applying a clockwise torque of 20 Ncm. If the implant does not rotate with torque application, stabilization will be considered a success of the device and the event will be logged as a "success of immediate stabilization" with time since mixing noted. Should the implant rotate with torque application, the implant will be removed, the osteotomy refreshed with the last drill used prior to implant placement, and a second application of TN-SM will be prepared per the IFU and injected into the site along with a new implant. After the TN-SM device cures for 20 minutes around the implant, implant stabilization will be tested a second time by applying a clockwise torque of 20 Ncm. If the implant does not rotate with torque application, stabilization will be considered a success of the device and the event will be logged as a "success of immediate stabilization" with time since mixing noted. Should the implant rotate with torque application again after the second application, stabilization will be considered a failure of the device and the event will be logged as a "failure of immediate stabilization" with time since mixing noted. The loosened implant will be removed. The remaining Tetranite will be removed by curetting or drilling the osteotomy until a bleeding bone surface is obtained. The clinician may place a wider or longer implant as appropriate for the tooth position. Otherwise the site will be grafted as per a conventional staged approach.
- The implant platform will be covered by seating a cover screw and the soft tissue will be reapproximated with monofilament sutures, as needed.

The Investigator will prescribe Chlorhexidine rinse in addition to medications for infection control and post-operative pain control according to his/her standard practice. Standard post-operative instructions will be provided, including the use of Chlorexidine and antibiotics These instructions will also include a description of dietary restrictions to only soft foods for a period of up to two weeks following surgery.

5.4 Post-Operative Follow-up (Visit 4)

The subject will return for a post-operative visit at 14 days (\pm 5 days) following implant placement for a general assessment of wound healing and to remove sutures, if applicable. In particular, the subject will have the following procedures and/or evaluations performed and documented at this visit:

- Dental and medical history
- Concomitant medication
- Adverse event check
- Oral hygiene evaluation
- CBCT Localized
- Intra-oral photographs
- Suture removal, if necessary

5.5 Implant Uncovering (Visit 5)

At 13 weeks (± 1 week) following implant surgery, the implant will be uncovered, the short-term implant stabilization will be checked, a healing or standard abutment will be placed, and the soft tissue adapted around the abutment. Short-term implant stabilization will be tested by applying a clockwise torque of 35 Ncm to the implant. If the implant does not rotate with torque application, stabilization will be considered a success of the device and the event will be logged as a "success of short-term stabilization". Should the implant rotate with torque application, the abutment will be removed, and the implant will be left and allowed to heal for an additional month and re-evaluated for successful integration. Lack of stabilization will be considered a failure of the device and the event will be logged as a "failure of short-term stabilization". In particular, the subject will have the following procedures and/or evaluations performed and documented at this visit:

- Dental and medical history
- Concomitant medication
- Adverse event check
- Oral hygiene evaluation
- Uncover implant, place healing abutment
- Implant stability by clockwise torque with maximum of 35 Ncm to confirm stabilization
- Standardized periapical radiograph
- Intra-oral photographs

5.6 Restorative Records (Visit 6)

At 3 weeks (+/- 2 weeks) following uncovering impressions/records will be taken for fabrication of a definitive crown restoration. In particular, the subject will have the following procedures and/or evaluations performed and documented at this visit:

- Dental and medical history
- Concomitant medication
- Adverse event check
- Oral Hygiene Evaluation
- Restorative Records
- Standardized periapical radiograph
- Intra-oral photographs

5.7 Insertion of Definitive Restoration (Functional Loading) (Visit 7, Baseline)

At 4 - 6 months after implant surgery, and contingent upon good stability, the study implant will be loaded with an abutment and crown restoration in appropriate occlusion. The subject will have the following procedures and/or evaluations performed and documented at this visit:

- Dental and medical history
- Concomitant medication
- Adverse event check
- Oral hygiene evaluation
- Periodontal measurements
- Insertion of definitive restoration
- Standardized periapical radiograph
- CBCT localized
- Intra-oral photographs
- Subject satisfaction

5.8 3-Month Follow-up (Visit 8)

Subjects will return at 3 months (± 2 weeks) post-loading for brief evaluation of the implant supported definitive restoration and check possible adverse events. The subject will have the

following procedures and/or evaluations performed and documented at this visit:

- Dental and medical history
- Concomitant medication
- Adverse event check
- Oral Hygiene evaluation
- Periodontal measurements
- Standardized periapical radiograph
- CBCT localized
- Intra-oral photographs
- Implant success
- Subject satisfaction

5.9 6-Month Follow-Up (Visit 9, Primary Endpoint)

Subjects will return at 6 months (\pm 1 month) post-loading for an evaluation of the implant supported definitive restoration and check possible adverse events. The subject will have the following procedures and/or evaluations performed and documented at this visit:

- Dental and medical history
- Concomitant medication
- Adverse event check
- Oral Hygiene evaluation
- Periodontal measurements
- Standardized periapical radiograph
- CBCT Localized
- Intra-oral photographs
- Implant success
- Subject satisfaction

5.10 9-Month Follow-Up (Visit 9.5)

Subjects will return at 9 months (± 1 month) post-loading for an evaluation of the implant supported

definitive restoration and check possible adverse events. The subject will have the following procedures and/or evaluations performed and documented at this visit:

- Dental and medical history
- Concomitant medication
- Adverse event check
- Oral Hygiene evaluation
- Periodontal measurements
- Intra-oral photographs
- Implant success
- Subject satisfaction

5.11 12-Month Follow-Up (Visit 10)

Subjects will return at 12 months (\pm 2 month) post-loading for an evaluation of the implant supported definitive restoration and check possible adverse events. The subject will have the following procedures and/or evaluations performed and documented at this visit:

- Dental and medical history
- Concomitant medication
- Adverse event check
- Oral Hygiene evaluation
- Periodontal measurements
- Standardized periapical radiograph
- CBCT Localized
- Intra-oral photographs
- Implant success
- Subject satisfaction

5.12 15-Month Follow-Up (Visit 11)

Subjects will return at 15 months (\pm 2 month) post-loading for an evaluation of the implant supported definitive restoration and check possible adverse events. The subject will have the following procedures and/or evaluations performed and documented at this visit:

- Dental and medical history
- Concomitant medication
- Adverse event check
- Oral Hygiene evaluation
- Periodontal measurements
- Intra-oral photographs
- Implant success
- Subject satisfaction

5.13 18-Month Follow-Up (Visit 12)

Subjects will return at 18 months (\pm 2 month) post-loading for an evaluation of the implant supported definitive restoration and check possible adverse events. The subject will have the following procedures and/or evaluations performed and documented at this visit:

- Dental and medical history
- Concomitant medication
- Adverse event check
- Oral Hygiene evaluation
- Periodontal measurements
- Standardized periapical radiograph
- Intra-oral photographs
- Implant success
- Subject satisfaction

5.14 21-Month Follow-Up (Visit 13)

Subjects will return at 21 months (\pm 2 month) post-loading for an evaluation of the implant supported definitive restoration and check possible adverse events. The subject will have the following procedures and/or evaluations performed and documented at this visit:

- Dental and medical history
- Concomitant medication
- Adverse event check

- Oral Hygiene evaluation
- Periodontal measurements
- Intra-oral photographs
- Implant success
- Subject satisfaction

5.15 24-Month Follow-Up (Visit 14)

Subjects will return at 24 months (\pm 2 month) post-loading for an evaluation of the implant supported definitive restoration and check possible adverse events. The subject will have the following procedures and/or evaluations performed and documented at this visit:

- Dental and medical history
- Concomitant medication
- Adverse event check
- Oral Hygiene evaluation
- Periodontal measurements
- Standardized periapical radiograph
- CBCT Localized
- Intra-oral photographs
- Implant success
- Subject satisfaction

5.16 Protocol Related Procedures

5.16.1 Early Withdrawal

Any subject may withdraw from the study at any time without prejudice and will be offered an alternative treatment for his/her dental condition. Subjects will be advised of the need for the prescribed follow-up visits for their ongoing care, well-being, and collection of any safety data.

The Investigator may withdraw any subject from the study in the case of:

- Non-compliance with the protocol
- Failure to attend the follow-up visits
- Serious Adverse Event (SAE) or adverse event, which in the opinion of the Investigator prevents

the subject's further participation in the study.

The subject withdrawal will be documented on a study termination form and must include the reason for the subject withdrawal. Efforts should be made to capture the primary study endpoint for each subject prior to withdrawal, if possible.

5.16.2 End of Study

Once the subject is seen for the final visit at 24-months post-functional loading, the subject will have completed the study. This will be documented on a study completion form.

5.16.3 Subject Replacement Policy

Subjects withdrawn from the study after enrollment will not be replaced.

5.16.4 Protocol Deviations

Deviations from the procedures established in the protocol are not permitted. If a deviation occurs, the study center must record the deviation on the appropriate CRF. The sponsor shall be notified immediately of any deviations in informed consent or Inclusion/Exclusion criteria. The IRB should be notified according to the requirements of the local IRB.

Any deviation from the protocol (including deviations from the expected study visit windows) may jeopardize the study outcome. Non-compliance of the subjects, as well as of the Investigators, may lead to the closure of the respective study center.

6 Evaluation of Adverse Events

For the avoidance of doubt, all AE/SAEs as defined below should be collected, fully investigated and documented in the source document and appropriate case report form for all subjects from the time of the signing of the informed consent until the last protocol-specific procedure. Documentation includes dates of event, treatment, outcome, assessment of seriousness and causal relationship to the device and/or study procedure (rationale to be provided).

6.1 Definitions

6.1.1 Adverse Event (AE)

An AE is defined as any untoward medical occurrence, unintended disease or injury, or any untoward clinical signs (including abnormal laboratory findings) in subjects, users or other persons, whether or not related to the investigational medical device or surgical procedure. This definition includes events related to the investigational medical device or events related to the procedures involved. For users or other persons, this definition is restricted to events related to investigational medical devices.

6.1.2 Serious Adverse Event (SAE)

Any adverse event that:

- led to a death
- led to a serious deterioration in the health of the subject, that either resulted in
 - o a life-threatening illness or injury, or
 - o a permanent impairment of a body structure or a body function, or
- in-patient or prolonged hospitalization, or
- medical or surgical intervention to prevent life-threatening illness or injury or permanent impairment to a body structure or a body function,
- led to fetal distress, fetal death, or a congenital abnormality or birth defect

NOTE: A planned hospitalization for a pre-existing condition, or a procedure required by the protocol, without serious deterioration in health, is not considered to be a serious adverse event.

NOTE: Implant failures requiring the removal of the implant are to be considered a serious adverse event.

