3.5 Study Sample Size

This study size will enroll 20 subjects, 10 at each of the two Research Centers. The enrollment will be capped at 20 subjects total and will not include control subjects.

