Contingent upon satisfactory stabilization, the implant will be loaded by the implant crown in appropriate occlusion with an abutment and crown prosthesis no sooner than four months and no later than six months after TN-SM device placement. A baseline standardized periapical image for documentation of crestal bone level and for evaluation of indicators of encapsulation will be captured. Photographic records will be captured of the study site before and after the crown is inserted from lingual (or palatal) and from buccal aspects. If the definitive restoration is inserted provisionally at this time, the provisional insertion date will be treated as the baseline loading date for the purposes of the study and the definitive insertion visit will be recorded as a separate visit.

Any loosened implants that are identified during the course of the study will be considered a failure and will be removed. The remaining Tetranite material will be removed by curetting or drilling the osteotomy until a bleeding bone surface is obtained. The clinician may place a wider or longer implant as appropriate for the tooth position. Otherwise the site will be grafted as per a conventional staged approach.

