6.3.5 SADE Reporting

In the occurrence of a serious adverse device effect, expedited reporting requirements are followed. The SAE case report form should be completed within 24 hours of awareness of the event in the EDC system. RevBio will receive an automated notification generated by the EDC system.

The product safety officer at RevBio will work with the Investigator to determine whether the event is anticipated (ASADE) or unanticipated (USADE). In case of USADE, the investigator must promptly notify its reviewing IRB as soon as possible, but no later than ten (10) working days after first learning of the event.

Since this is a multi-center study, RevBio will inform investigators at all participating centers of any reported USADEs related to this protocol and the study device. Copies of such external USADE reports should be forwarded to the IRB for review and a copy must be kept in the investigator site files.

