7.1 Analysis of Primary Endpoints

The primary endpoint in this pilot study will be summarized descriptively and no hypothesis tests are planned.

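### The protocol does not say consistently whether removing an implant after a failed first TN-SM application is a serious adverse event, so the two centers can report the same event differently

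*Combined protocol and SAP*

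**What the plan says.** Four places in the protocol bear on the same event.

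- **Section 5.3.4** covers the first torque test, at 20 Ncm: "Should the implant rotate with torque application, the implant will be removed, the osteotomy refreshed with the last drill used prior to implant placement". A second TN-SM application and a new implant follow, and the test is repeated. If the new implant does not rotate, "stabilization will be considered a success of the device and the event will be logged as a" success of immediate stabilization. A failure entry is prescribed only at the next step: "Should the implant rotate with torque application again after the second application, stabilization will be considered a failure of the device".
- **Section 3.9** states a general rule: "Any loosened implants that are identified during the course of the study will be considered a failure and will be removed". It makes no exception for a first attempt.
- **Section 6.1.2, second note:** "Implant failures requiring the removal of the implant are to be considered a serious adverse event".
- **Section 6.1.2, first note** takes out of the SAE definition a procedure that the protocol requires, provided that health has not seriously deteriorated.

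If the event is an SAE and is related to the device, Section 6.3.5 applies: "The SAE case report form should be completed within 24 hours of awareness of the event in the EDC system". Section 6.4 then sends it to the Clinical Events Committee (CEC), which adjudicates reported SAEs.

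**The concern.** By the first torque test the subject is enrolled (Section 3.8 enrolls once the extraction-site criteria are met) and has been exposed to TN-SM. A rotation at that test is the earliest sign of how the device performs, and the re-treated subject has a second exposure and repeat drilling. Device-attributed events are the first secondary endpoint (Section 2.2.1), and safety is a stated aim of the pilot.

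One center could join Section 3.9 to the second 6.1.2 note and file an expedited SAE. The other could follow Section 5.3.4, rely on the first 6.1.2 note, and record a success with no SAE. Both would have followed the text. The SAE and serious adverse device effect (SADE) counts, and the cases that reach the CEC, would then partly reflect which passage a center read.

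**Working it through.** **Inputs.** From Section 3.5: "This study size will enroll 20 subjects, 10 at each of the two Research Centers". From Section 7.1: "The primary endpoint in this pilot study will be summarized descriptively and no hypothesis tests are planned". There is no alpha, power or target rate to reproduce. The only figure that can be checked is the sample size, 2 × 10 = 20, and it agrees.

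**Step 1: the passages side by side, for an implant that rotates at the first test and is removed.**

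| Place | What it implies |
|---|---|
| 3.9 | A failure, if the implant counts as loosened |
| 3.11.1 | Implant mobility is a failure for study purposes |
| 5.3.4 | Remove, re-treat and retest; failure is logged only after a second rotation |
| 6.1.2, first note | Not an SAE, if the removal is a protocol-required procedure without serious deterioration |
| 6.1.2, second note | An SAE, if the removal is an implant failure requiring removal |

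**Step 2: two readings, each of which can be built from the text.**

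- *Reading A.* Section 5.3.4 uses the word loosened for an implant that has rotated under this same test at the second attempt. Applied to the first attempt, 3.9 makes it a failure and the second 6.1.2 note makes its removal an SAE. Section 6.1.3 counts any malfunction, and any event with even a possible device relationship, as an adverse device effect, so the event would very likely be a SADE.
- *Reading B.* Section 5.3.4 is the specific rule. It prescribes the first removal as a step and keeps failure for the second rotation. The first 6.1.2 note then takes the removal out of the SAE definition.

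No sentence chooses between A and B.

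**Step 3: size.** Let k be the number of subjects whose first application fails, whose second holds, and who have no other SAE. A subject whose second application also fails is logged as a failure and is not in k.

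- Change in the trial's subject-level SAE rate = k/20, which is 1/20 = 5 points per subject.
- Change within a center = k/10, which is 1/10 = 10 points per subject.

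| k | SAE subjects from this source, reading B | Reading A | Reading A, exact 95% interval |
|---|---|---|---|
| 1 | 0/20 = 0% | 1/20 = 5% | 0.1% to 24.9% |
| 2 | 0/20 = 0% | 2/20 = 10% | 1.2% to 31.7% |
| 3 | 0/20 = 0% | 3/20 = 15% | 3.2% to 37.9% |

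The exact (Clopper-Pearson) interval for 0/20 is 0% to 16.8%. These intervals are added here for scale; the protocol plans none.

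The same k moves the immediate-stabilization count. With k = 2 and no other failures, it is 20/20 = 100% if only 5.3.4 is followed, and (20 − 2)/20 = 90% if 3.9 is applied.

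**Step 4: would the case arise at all?** The documents give no first-failure rate. For an assumed rate q, the chance of at least one first failure in 20 subjects is 1 − (1 − q)^20: 64% at q = 5%, 88% at 10%, 99% at 20%, and above 99% at 30%. These rates are assumptions that only show the range. The protocol does foresee the event, because it writes out the second application.

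**The case against.** The strongest reply is that the protocol has a gap and no contradiction, and much of that reply stands.

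- The first 6.1.2 note gives a natural route to no SAE. The second note would still cover removals for infection, radiolucency or lost integration, and final stabilization failures.
- The clean-out and salvage text that follows the 3.9 rule matches what 5.3.4 prescribes after the second failure, and it contains no re-application step. The authors may have meant definitive failure only.
- Rotation under torque does not always lead to removal: Section 5.5 leaves an implant that rotates at 35 Ncm to heal for another month. Removal during surgery is not failure in itself either, because every enrolled subject's trial implant is removed before TN-SM is applied.
- The success entry in 5.3.4 does not displace Section 6. All AEs and SAEs are collected from consent, all device deficiencies are reportable (Sections 4.2 and 6.3.3), surgical details are listed (Section 7.4.1), and monitors check event reporting (Section 9.3.2).

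A reader might therefore infer too much: that the first removal is an SAE which the protocol hides as a success. The documents do not support that. SAE status follows only by joining 3.9 to the second 6.1.2 note and passing over the first, and success is only the stabilization entry that 5.3.4 prescribes.

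What survives is narrower. Section 3.9 says any. None of the reporting routes says whether a first-test rotation qualifies. A listing or an accountability log is not an event count and does not trigger the 24-hour form.

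**Conclusion.** The concern holds as an inconsistency in safety classification. Sections 3.9 and 5.3.4 and the two 6.1.2 notes do not give one answer for an implant removed after a failed first application. The size is 5 percentage points of the trial's SAE rate per affected subject, or 10 points within a center, assuming that the second application holds and the subject has no other SAE. The total depends on a first-failure rate that the documents do not give. A contrast such as 10% to 30% against 0% would only restate an assumed rate.

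Two further inferences should be avoided. First, no planned test or numeric stopping boundary turns on this count: the analysis is descriptive, and early termination under Section 9.4 is discretionary and has no threshold. Second, the point concerns how the first removal is classified for safety; how the primary composite should score a re-treated subject is a separate question that it does not settle. The point is worth correcting because the trial is small, device-attributed events are its first secondary endpoint, and the pilot is meant to try out measures for a larger study.

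**What to change.** 1. Reconcile Section 3.9, Section 5.3.4 and both notes in Section 6.1.2, so that one passage states whether removal after a failed first application is an SAE or SADE. This review takes no position on which rule to adopt.
2. Whichever is adopted, record each first-test rotation as its own event on the eCRF.
3. Report one-application and two-application subjects separately in the stabilization summary and in the Section 7.3 safety tables.
4. Apply CEC adjudication only if the event is classified as an SAE, which keeps to the committee's remit in Section 6.4.

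The cost is a short wording change, one eCRF field and one table split. The downside is a possibly less favourable reported device-performance or SAE count, and a little extra data entry.
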